### 16.1.2. ALL TEAEs

Number of subjects, percentages, number of events and patient-year incidence rate of TEAEs will be presented by System Organ Class (SOC) and Preferred Term (PT) and also broken down further by maximum severity, relationship to trial medication and subgroups (refer to section 7.5.1).

A summary of 1297.2 trial TEAEs occurring during the 1297.3 screening phase will be prepared.

#### 16.1.2.1. Intensity

Intensity is classified as mild/ moderate/ severe (increasing intensity). TEAEs starting after the first dose of trial medication with a missing intensity will be classified as severe. If a subject reports a TEAE more than once within that SOC/ PT, the AE with the worst case intensity will be used in the corresponding intensity summaries.

---

Document: \\ieedc-nas01a\BIOSdata\Boehringer\_Ingelheim\BI\_695501\NVA96235\Biostatistics\Documentation\SAP\10  
v1.0\BI\_1297.3\_SAP\_22JUN2016\_v1.0

Author: Version Number: 1.0  
Version Date: 22JUN2016

Template No: CS\_TP\_BS016 – Revision 3  
Effective Date: 01May2012

Reference: CS\_WI\_BS005

#### 16.1.2.2. Relationship to Trial Medication

An investigator-assessed drug-related AE is defined as an AE with a relationship to trial medication ticked "yes" according to the investigator. TEAEs with a missing relationship to trial medication will be regarded as related to trial medication. If a subject reports the same AE more than once within that SOC/PT, and at least 1 episode is related, the AE will be considered related for the corresponding relationship summaries.

All drug related AEs will be listed.

#### 16.1.3. TEAEs LEADING TO DISCONTINUATION OF TRIAL MEDICATION

TEAEs leading to permanent discontinuation of trial medication will be identified by using the "Action taken with trial drug due to AE?" equal to "Drug Withdrawn" from AEs eCRF pages.

For TEAEs leading to permanent discontinuation of trial medication, number of subjects, percentages, number of events and patient-year incidence rate by SOC and PT will be prepared.

The AEs causing treatment modification or Drug Withdrawn will be listed.

#### 16.1.4. SERIOUS ADVERSE EVENTS

Serious adverse events (SAEs) are those events recorded as "Serious" on the AEs page of the eCRF. A summary of serious TEAEs by SOC and PT will be prepared.

Number of subjects, percentages, number of events and patient-year incidence rate of Serious TEAEs by SOC and PT will be prepared.

Number of subjects, percentages, number of events and patient-year incidence rate of Non-Serious TEAEs with incidence in preferred terms strictly greater than 5% in at least one of treatment groups by SOC and PT will be prepared.

The SAEs and Non-SAEs will be listed.

#### 16.1.5. RELATED SERIOUS ADVERSE EVENTS

Number of subjects, percentages, number of events and patient-year incidence rate of Related Serious TEAEs by SOC and PT will be prepared.

#### 16.1.6. ADVERSE EVENTS LEADING TO DEATH

TEAEs leading to Death are those events which are recorded as "Results in death" or with outcome "Fatal" on the AEs page of the eCRF. Number of subjects, percentages, number of events and patient-year incidence rate of TEAEs leading to death by SOC and PT will be prepared.

All AEs leading to death will be listed.

---

Document: \\ieedc-nas01a\BIOSdata\Boehringer\_Ingelheim\BI\_695501\NVA96235\Biostatistics\Documentation\SAP\10  
v1.0\BI\_1297.3\_SAP\_22JUN2016\_v1.0

Author: Version Number: 1.0  
Version Date: 22JUN2016

Template No: CS\_TP\_BS016 – Revision 3  
Effective Date: 01May2012

Reference: CS\_WI\_BS005

Copyright © 2012 . All rights reserved.  
The contents of this document are confidential and proprietary to  
reproduction is strictly prohibited.

. Unauthorized use, disclosure or

### **16.1.7. ADVERSE EVENTS OF SPECIAL INTEREST**

An overall summary of the number of subjects, percentages, number of events and patient-year incidence rate within each of the categories described in the sub-section below will be provided by SOC and PT.

#### **16.1.7.1. Reported by investigator**

AESI reported by investigators are those events recorded as "Adverse Event of Special Interest" equal to "Yes" on the AEs page of the eCRF.

#### **16.1.7.2. Infections and Serious Infections**

Infections are those events with a SOC equal to "Infections and infestations".

Serious infections are:

- AEs which are both infections and SAEs as reported on the AEs page of the eCRF.
- AEs which are both infections and identified by medical advisor as requiring class IV (intravenous) antibiotics.

Serious infections events of special interest are those events both identified as serious infections adverse events and recorded as "Adverse Event of Special Interest" equal to "Yes" on the Adverse Events page of the eCRF.

Treatment Emergent Infections / Serious Infections will be tabulated separately.

Infections / Serious Infections will be listed.

#### **16.1.7.3. Hypersensitivity reactions**

Hypersensitivity reactions are those events recorded as MedDRA code in the pre-defined Standardized MedDRA Queries (SMQ) "Hypersensitivity" (narrow).

Hypersensitivity reactions adverse events of special interest are those events both identified as Hypersensitivity reactions adverse events and recorded as "Adverse Event of Special Interest" equal to "Yes" on the Adverse Events page of the eCRF.

Treatment Emergent Hypersensitivity reactions will be tabulated separately.

Hypersensitivity reactions will be listed.

#### **16.1.7.4. Drug Induced Liver Injury (DILI)**

Drug Induced Liver Injury (DILI) are those events identified by medical advisor on the subset of AEs for subjects presenting laboratory potential DILI findings (refer to section 16.3).

DILI events of special interest are those events both identified as DILI adverse events and recorded as "Adverse Event of Special Interest" equal to "Yes" on the Adverse Events page of the eCRF.

---

Document:	\ieedc-nas01a\BIOSdata\Boehringer_Ingelheim\BI_695501\NVA96235\Biostatistics\Documentation\SAP\10\		
Author:		Version Number:	1.0

Template No: CS\_TP\_BS016 – Revision 3  
Effective Date: 01May2012

Reference: CS\_WI\_BS005

Copyright © 2012 . All rights reserved.  
The contents of this document are confidential and proprietary to . Unauthorized use, disclosure or  
reproduction is strictly prohibited.

Treatment Emergent DILI will be tabulated separately.

Drug Induced Liver Injury (DILI) will be listed.

#### 16.1.7.5. Injection-site reactions

Injection-site reactions are those events recorded with MedDRA high level terms (as listed in BI SMQs

Administration site reaction subsearches 1,2,4 and 5, refer to APPENDIX 5):

- Administration site reactions NEC
- Application and instillation site reactions
- Injection site reactions
- Infusion site reactions

The number and percentage of subjects with injection site reactions will be summarized by treatment for each injection site reaction (swelling, induration, heat, redness, pain, itching, bruising, other).

Treatment Emergent Injection-site reactions as well as injections site reactions types will be tabulated separately.

Treatment Emergent Injection-site reactions as well as injections site reactions types will be listed.

#### 16.1.7.6. Anaphylactic reactions

Anaphylactic reactions are those events recorded as MedDRA code in the pre-defined Standardized MedDRA Queries (SMQ) = "Anaphylactic reactions" (narrow).

Anaphylactic reactions adverse events of special interest are those events both identified as Anaphylactic reactions and recorded as "Adverse Event of Special Interest" equal to "Yes" on the Adverse Events page of the eCRF.

Treatment Emergent Anaphylactic reactions will be tabulated separately.

Anaphylactic reactions will be listed.

#### 16.1.8. AEs OCCURRING AFTER THE LAST INJECTION FOR SUBJECTS DISCONTINUED DUE TO LACK OF EFFICACY.

Subjects who discontinued treatment due to lack of efficacy will be identified from "End of treatment visit" eCRF page, where "Reason for End of Treatment" is "Lack of Efficacy".

Number of subjects, percentages, number of events and patient-year incidence rate of AEs occurring after the last injection and prior to the last injection + 10 weeks for subjects discontinued due to lack of efficacy by SOC and PT will be prepared.

AEs occurring after the last injection and prior to the last injection + 10 weeks for subjects discontinued due to lack of efficacy will be listed.

---

Document: \\ieedc-nas01a\BIOSdata\Boehringer\_Ingelheim\BI\_695501\NVA96235\Biostatistics\Documentation\SAP\10  
v1.0\BI\_1297.3\_SAP\_22JUN2016\_v1.0

Author: Version Number: 1.0  
Version Date: 22JUN2016

Template No: CS\_TP\_BS016 – Revision 3  
Effective Date: 01May2012

Reference: CS\_WI\_BS005

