### 16.1.1. ADVERSE EVENT SPECIFIC DERIVATION

#### 16.1.1.1. Treatment Emergent Adverse Event

Treatment-emergent adverse events (TEAEs) are defined as AEs that started or worsened in severity on or after the first dose of 1297.3 trial medication and prior to the last date of 1297.3 trial medication + 10 weeks inclusive.

Non-TEAEs will be classified as "Prior treatment" if AE start date is strictly prior the first injection date. Non-TEAEs will be classified as "Post treatment" if AE start date is strictly after the last injection date + 70 days.

See APPENDIX 2 for handling of partial dates for AEs. In the case where it is not possible to define an AE as treatment-emergent or not, the AE will be classified by the worst case; i.e. treatment-emergent.

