#### 16.1.1.2. Patient-Year incidence rate

Patient-year incidence rate per 1000 years for AEs will be calculated as follows:

(Number of subjects with at least one AE) / (Patient-Year) \* 1000

where Patient-Year is the sum of time at risk for each subject (days) in the treatment group divided by 365.25.

The time at risk (years) per subject is derived as following:

- subject had at least one AE with specific criterion:

time at risk (days) = start date of first AE meeting the specific criterion – start of treatment +1

- subject without AE with specific criterion:

time at risk (days) = end of treatment + 70 – start of treatment +1

Patient-year incidence rate per 1000 years for TEAEs, SAEs, related TEAEs, TEAEs leading to discontinuation of trial medication, TEAEs leading to Death and AEs of special interest (AESI) will be calculated using the above algorithm.

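### The rate of AEs after the last injection in patients stopped for lack of efficacy has no time at risk of its own, and the SAP's default clock counts treatment time in which the event cannot occur.

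*SAP*

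**What the plan says.** SAP 16.1.8 defines a supportive safety output. Its population is set by the sentence beginning "Subjects who discontinued treatment due to lack of efficacy will be identified from", which points to the reason for end of treatment in the eCRF. For these subjects it requests numbers of subjects, percentages, numbers of events and the "patient-year incidence rate of AEs occurring after the last injection and prior to the last injection + 10 weeks", by system organ class and preferred term. It does not say when time at risk starts or ends.

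The rate itself is defined only in SAP 16.1.1.2, which opens with "Patient-year incidence rate per 1000 years for AEs will be calculated as follows" and divides the number of subjects with at least one AE by patient-years. For a subject with the event, "time at risk (days) = start date of first AE meeting the specific criterion – start of treatment +1". For a subject without it, "time at risk (days) = end of treatment + 70 – start of treatment +1". The denominator is described by the words "where Patient-Year is the sum of time at risk for each subject (days) in the treatment group divided by 365.25".

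SAP 3.3 records no change from the protocol. Protocol 7.3.1 and 7.3.4 mention incidence per 1000 patient-years but set out no way of computing time at risk.

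**The concern.** Numerator and denominator cover different periods. An AE counts in 16.1.8 only if it starts after the last injection and within 10 weeks of it. Both branches of the 16.1.1.2 rule start at the first dose, so the whole span from first to last injection is counted as time at risk when it is not.

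Two consequences follow. The rate is always pulled downwards, that is, towards reassurance. It also falls mechanically with longer treatment before stopping, so groups with the same experience after the last injection show different rates if they stopped at different times. The table is the only output in the SAP text that isolates AEs after treatment ended for lack of efficacy, and a reader would take its rate column at face value.

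**Working it through.** The documents state no numerical rate for this output, so there is no planned figure to reproduce. The check compares the two denominators; the numerator is the same in both.

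**Inputs**
- Window: 10 weeks, or 70 days, after the last injection (SAP 16.1.8 and 16.1.1.2).
- Time-at-risk formulas: SAP 16.1.1.2, reading end of treatment as the date of the last injection.
- T = days from first to last injection. Not given for patients who stop for lack of efficacy, so a range is shown.
- d = days from last injection to first qualifying AE. Not given; 35 is assumed in the illustration.

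**Formulas**
- SAP clock: T + 70 + 1 = T + 71 days without an event; T + d + 1 days with one.
- Clock confined to the window: 70 days without an event; d days with one.

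**Event-free patient, factor (T + 71)/70**

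| Time from first to last injection | T (days) | SAP time (days) | Factor |
|---|---|---|---|
| 2 weeks | 14 | 85 | 1.2 |
| 4 weeks | 28 | 99 | 1.4 |
| 10 weeks | 70 | 141 | 2.0 |
| 12 weeks | 84 | 155 | 2.2 |
| 24 weeks | 168 | 239 | 3.4 |
| 40 weeks | 280 | 351 | 5.0 |

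For a patient with an event the factor is (T + d + 1)/d. At T = 168 and d = 35 it is 204/35 = 5.8.

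**Illustration (assumed): 10 patients, T = 168 for all, 3 with a first AE at d = 35**
- SAP clock: 3 × 204 + 7 × 239 = 2285 days; 2285/365.25 = 6.256 patient-years; 3/6.256 × 1000 ≈ 480.
- Window clock: 3 × 35 + 7 × 70 = 595 days; 595/365.25 = 1.629 patient-years; 3/1.629 × 1000 ≈ 1842.
- Ratio: 2285/595 = 3.84.

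**Dependence on prior treatment, same 10 patients and same events**
- T = 84: 3 × 120 + 7 × 155 = 1445 days, or 3.956 patient-years; SAP rate about 758.
- T = 280: 3 × 316 + 7 × 351 = 3405 days, or 9.322 patient-years; SAP rate about 322.
- The window rate is 1842 in both cases.

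**Averaged over stopping times (assumed).** With last injections spread evenly over weeks 2 to 46 and a constant true rate of 0.5 to 4 per patient-year, simulation gives an overall factor of 3.5 to 4.4.

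**The case against.** The strongest objection is that the application of 16.1.1.2 to this table is inferred. That section ends with a list of the outputs it governs, closing with "TEAEs leading to discontinuation of trial medication, TEAEs leading to Death and AEs of special interest (AESI) will be calculated using the above algorithm", and the 16.1.8 output is not on the list. SAP 8 also leaves table format and content to templates that are not part of the text available here, so a table-specific denominator in a template cannot be excluded. Both points stand as qualifications, but they do not rescue the plan. The section is introduced for AEs in general and written for any specific criterion. Events in 16.1.8 are treatment-emergent by the SAP's own definition, whose window is "on or after the first dose of 1297.3 trial medication and prior to the last date of 1297.3 trial medication + 10 weeks inclusive", and TEAEs are on the list. If 16.1.1.2 is held not to apply, the requested rate has no defined time at risk at all.

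The second objection is that the impact is small. The analyses are descriptive (Protocol 7.2, SAP 6.5), the counts of subjects and events in the table do not depend on the clock, and every such AE is listed with its study day (SAP 16.1.8 and 6.1). This stands and limits the severity.

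Three stronger readings are tempting, and the documents do not support them:
- A reader might infer from the treatment-group wording in 16.1.1.2 that patients who never stopped for lack of efficacy also enter the denominator. The heading, identification rule and table sentence of 16.1.8 all confine the output to the lack-of-efficacy subjects, so that reading is strained. The section would still be clearer if it named its denominator.
- A reader might call the understatement several-fold without condition. It is below 2 for an event-free patient whose last injection falls before about week 10.
- A reader might set this rate against purely on-treatment rates elsewhere. The other rates are TEAE rates, which already include the 70 days after the last dose, and no such comparison is planned.

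**Conclusion.** Wrong as written, minor. Following the SAP text puts time in which the event cannot occur into the denominator of the 16.1.8 rate, and the error always lowers it. For event-free patients the factor runs from about 1.2 after 2 weeks on treatment to about 5.0 after 40 weeks; it is larger for patients with an event. In the 24-week illustration it is 3.84. These sizes rest on three things: applying the 16.1.1.2 algorithm to this output, reading end of treatment as the last injection, and assumed stopping and event times.

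The damage is confined to one rate column in one descriptive table. A reader might infer that the trial's main safety result is affected. It is not: the primary endpoint is the number and proportion of patients with drug-related AEs (Protocol 7.3.1, SAP 16) and uses no patient-years.

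**What to change.** Add two statements to SAP 16.1.8:
1. The denominators for n, percentages and patient-years are the subjects who discontinued treatment due to lack of efficacy.
2. Time at risk runs from the day after the last injection to the first qualifying AE or, if there is none, to the earlier of last injection + 70 days and end of follow-up (death, withdrawal or loss to follow-up).

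The end-of-follow-up limit is needed because patients may withdraw consent, die or be lost before the 10-week visit (Protocol 3.3.4.1 and 6.2.3). Crediting them with a full 70 days would again overstate time at risk.

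The cost is two sentences and a separate derivation for one table. No new data collection should be needed. The displayed rate will be higher than under the present rule, so a table footnote should state its time at risk, which differs from that of the other AE tables.

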### **16.1.9. NON-SERIOUS ADVERSE EVENTS LEADING TO DISCONTINUATION OF TREATMENT**

Non-serious adverse events leading to discontinuation of treatment (recorded as “Is this a serious adverse event?” equal to “No” and “Action taken with trial drug due to AE?” equal to “Drug Withdrawn” on the Adverse Events page of the eCRF).

Number of subjects, percentages, number of events and patient-year incidence rate of treatment emergent non-serious adverse events leading to discontinuation of treatment by SOC and PT tables will be prepared.

Non-serious adverse events leading to discontinuation of treatment will be listed.

### **16.1.10. FURTHER SELECTED ADVERSE EVENTS**

Further selected adverse events were not defined in the CTP and were identified to support a project-level integrated safety summary of additional important safety topics of the class.

#### **16.1.10.1. Hepatitis B Virus (HBV) reactivation**

Hepatitis B Virus (HBV) reactivation are those events recorded as MedDRA LLT search “reactivation of hepatitis B”.

Number of subjects, percentages, number of events and patient-year incidence rate of Treatment Emergent Hepatitis B Virus (HBV) reactivation by SOC and PT tables will be prepared.

Hepatitis B Virus (HBV) reactivation will be listed.

#### **16.1.10.2. Haematological disorders**

Haematological disorders are those events recorded as:

- BlcMQ “Haematologic disorders” (narrow and broad)(refer to APPENDIX 5)

Number of subjects, percentages, number of events and patient-year incidence rate of Treatment Emergent Haematological disorders by SOC and PT tables will be prepared

Haematological disorders will be listed.

#### **16.1.10.3. Neurological events (Demyelinating disorders)**

Neurological events (Demyelinating disorders) are those events recorded as:

- SMQ “Demyelination” (narrow)

Number of subjects, percentages, number of events and patient-year incidence rate of Treatment Emergent Neurological events (Demyelinating disorders) by SOC and PT tables will be prepared.

Neurological events (Demyelinating disorders) will be listed.

---

Document: \\ieedc-nas01a\BIOSdata\Boehringer\_Ingelheim\BI\_695501\NVA96235\Biostatistics\Documentation\SAP\10  
v1.0\BI\_1297.3\_SAP\_22JUN2016\_v1.0

Author: Version Number: 1.0  
Version Date: 22JUN2016

Template No: CS\_TP\_BS016 – Revision 3  
Effective Date: 01May2012

Reference: CS\_WI\_BS005

#### 16.1.10.4. Systemic lupus erythematosus

Systemic lupus erythematosus are those events recorded as:

- SMQ "Systemic lupus erythematosus" (narrow)

Number of subjects, percentages, number of events and patient-year incidence rate of Treatment Emergent Systemic lupus erythematosus by SOC and PT tables will be prepared.

Systemic lupus erythematosus will be listed.

#### 16.1.10.5. Sarcoidosis

Sarcoidosis are those events recorded as:

- BlcMQ "Sarcoidosis" (narrow)

Number of subjects, percentages, number of events and patient-year incidence rate of Treatment Emergent Sarcoidosis by SOC and PT tables will be prepared.

Sarcoidosis will be listed.

#### 16.1.10.6. Stevens-Johnson syndrome

Stevens-Johnson syndrome are those events recorded as:

- PT "Stevens-Johnson syndrome"

Number of subjects, percentages, number of events and patient-year incidence rate of Treatment Emergent Stevens-Johnson syndrome by SOC and PT tables will be prepared.

Stevens-Johnson syndrome will be listed.

#### 16.1.10.7. Erythema multiforme

Erythema multiforme are those events recorded as:

- PT "Erythema multiforme"

Number of subjects, percentages, number of events and patient-year incidence rate of Treatment Emergent Erythema multiforme by SOC and PT tables will be prepared.

Erythema multiforme will be listed.

#### 16.1.10.8. Autoimmune hepatitis

Autoimmune hepatitis are those events recorded as:

- SMQ "Hepatitis, noninfectious" (narrow)

Number of subjects, percentages, number of events and patient-year incidence rate of Treatment Emergent Autoimmune hepatitis by SOC and PT tables will be prepared.

---

Document: \\ieedc-nas01a\BIOSdata\Boehringer\_Ingelheim\BI\_695501\NVA96235\Biostatistics\Documentation\SAP\10  
v1.0\BI\_1297.3\_SAP\_22JUN2016\_v1.0

Author: Version Number: 1.0  
Version Date: 22JUN2016

Template No: CS\_TP\_BS016 – Revision 3  
Effective Date: 01May2012

Reference: CS\_WI\_BS005

Copyright © 2012 . All rights reserved.  
The contents of this document are confidential and proprietary to  
reproduction is strictly prohibited.

. Unauthorized use, disclosure or

---

Autoimmune hepatitis will be listed.

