## 4.2 CONCOMITANT THERAPY, RESTRICTIONS, AND RESCUE TREATMENT

### 4.2.1 Rescue medication, emergency procedures, and additional treatment(s)

Patients will continue to take their usual prescribed concomitant medications as allowed by the CTP, including MTX (within the dose range of the 1297.2 trial, up to Week 12) from their usual source. After Week 12, the dosing regimen for MTX and associated folic acid or folinic acid intake may be adjusted at the Investigator's discretion. In this case, MTX treatment can be combined with or replaced by other non-biologic DMARDs (as described in [Table 4.2.2.1: 1](#)). Non-biologic DMARD therapy may be modified during the trial, per Investigator assessment. Certain side effects are commonly associated with MTX treatment and therefore patients are required to take folic acid (a stable dose of at least 5 mg/week or as per local practice) or folinic acid (at least 1 mg/week or as per local practice), from their usual source, to minimize MTX-related toxicity.

All patients should also continue to receive any oral nonsteroidal anti-inflammatory drugs (NSAIDs) at a stable dose or background oral corticosteroids as required throughout the trial. There are no special emergency procedures to be followed.

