#### 16.1.10.10. Chronic heart failure

Chronic heart failure are those events recorded in SMQ "Cardiac failure" (narrow).

Number of subjects, percentages, number of events and patient-year incidence rate of Treatment Emergent Chronic heart failure by SOC and PT tables will be prepared.

Chronic heart failure will be listed.

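### 'Autoimmune hepatitis' and 'Chronic heart failure' are each counted with a search broader than the title, so their totals and rates may overstate the named risk

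*SAP*

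**What the plan says.** SAP 16.1.10 adds ten categories of selected adverse events and explains their status: "Further selected adverse events were not defined in the CTP and were identified to support a project-level integrated safety summary". Each category is tabulated by system organ class and preferred term (patients, percentages, events, patient-year rate) and is also listed.

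- **16.1.10.8.** The definition begins "Autoimmune hepatitis are those events recorded as" and names one search, the narrow scope of the SMQ *Hepatitis, noninfectious*. The output keeps the autoimmune title: "patient-year incidence rate of Treatment Emergent Autoimmune hepatitis by SOC and PT tables will be prepared".
- **16.1.10.10.** "Chronic heart failure are those events recorded in SMQ" *Cardiac failure*, narrow scope. Its tables and listing are titled chronic heart failure.
- **16.1.10.1.** "Hepatitis B Virus (HBV) reactivation are those events recorded as MedDRA LLT search", followed by one term, reactivation of hepatitis B. No term group, laboratory rule or medical review is added.

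**The concern.** The titles of the first two categories name a specific diagnosis, while the searches behind them are named for a wider group of conditions. A non-infectious hepatitis of another cause, or a cardiac failure that is not chronic, would be counted under the specific title if its term lies in the narrow SMQ.

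At stake is the category total, which is the figure most likely to be carried into an integrated summary. The report could also disagree with itself. Under SAP 16.1.7.4 the medical advisor identifies drug-induced liver injury among the adverse events of patients with qualifying liver findings. If such an event is also coded within the hepatitis SMQ, one table would call it drug-induced and another autoimmune.

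For hepatitis B the question is sensitivity. Protocol 2.3 says some reactivations have been fatal, so a missed case would matter.

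**Working it through.** The documents give no figure to reproduce here. The check is a comparison of texts, followed by a calculation for scale.

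**Step 1. Title against search, SAP 16.1.10.1 to 16.1.10.10**

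| Section | Title | Search | Same concept by name? |
|---|---|---|---|
| .1 | HBV reactivation | one LLT, reactivation of hepatitis B | yes |
| .2 | Haematological disorders | BIcMQ Haematologic disorders | yes |
| .3 | Demyelinating disorders | SMQ Demyelination (narrow) | yes |
| .4 | Systemic lupus erythematosus | SMQ of that name (narrow) | yes |
| .5 | Sarcoidosis | BIcMQ Sarcoidosis (narrow) | yes |
| .6 | Stevens-Johnson syndrome | PT of that name | yes |
| .7 | Erythema multiforme | PT of that name | yes |
| .8 | Autoimmune hepatitis | SMQ Hepatitis, noninfectious (narrow) | **no, search wider** |
| .9 | Malignancies | BIcMQ Malignancies | yes |
| .10 | Chronic heart failure | SMQ Cardiac failure (narrow) | **no, search wider** |

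Two of the ten titles are narrower than their search. The SAP has tools for more specific definitions: single preferred terms (.6, .7) and identification by the medical advisor (16.1.7.2 for infections needing intravenous antibiotics, 16.1.7.4 for liver injury).

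**Step 2. Direction**

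Let S be the number of patients with any event in the SMQ, and T the number among them who have the titled diagnosis. The category reports S, and S ≥ T. They are equal only if every patient counted has the titled diagnosis. Overstatement is therefore possible, and it occurs only if at least one patient qualifies solely through other events.

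**Step 3. Scale of one patient**

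Inputs:
- N = 300 to 400 (protocol 7.7).
- Last dose on Day 337 (protocol flow chart).
- Time at risk without an event = end of treatment + 70 − start + 1 days, and rate = patients with an event ÷ patient-years × 1000 (SAP 16.1.1.2).

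Assumptions: all patients are treated and receive the Day 337 dose, and the 16.1.1.2 rate applies to the selected events, which that section does not list by name.

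- Days at risk: 337 − 1 + 70 + 1 = 407, and 407/365.25 = 1.114 years.
- N = 300: 300 × 407/365.25 = 334.3 patient-years. One patient is 1/300 = 0.33% and 1000/334.3 = 2.99 per 1000 patient-years.
- N = 400: 400 × 407/365.25 = 445.7 patient-years. One patient is 1/400 = 0.25% and 1000/445.7 = 2.24 per 1000 patient-years.

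Early dropout lowers the patient-years and raises the effect per patient.

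**Step 4. Hepatitis B**

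The term searched and the title name the same event, so nothing is mislabelled. The remaining question is whether a reactivation could be coded to a different hepatitis B term and not be retrieved. The documents do not list the terms, so neither the chance nor the number can be derived.

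**The case against.** The strongest reply is that this is a matter of headings. Tables by preferred term show each event under its own term, with its own count. All treatment-emergent events are tabulated the same way under SAP 16.1.2. Liver injury has separate laboratory criteria (16.3.1) and medical review (16.1.7.4). The categories lie outside the protocol's endpoints, and changing searches in one trial could break alignment with the project-level summary. This stands as a limit on the harm. It does not correct the category total or its rate, which still carry the wrong name.

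A further reply is that a single preferred term for autoimmune hepatitis could itself miss cases. That is fair, and it is why the SMQ output should be kept under its own name.

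Several stronger readings are tempting but are not supported:

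- **A reader might infer that every non-infectious hepatitis, or the whole cardiac failure SMQ, is counted.** Only the narrow scopes are used.
- **A reader might infer that methotrexate hepatitis will appear as autoimmune.** Protocol 4.2.1 says only "Certain side effects are commonly associated with MTX treatment" and refers to methotrexate toxicity in general. It does not name hepatitis.
- **A reader might infer that hepatitis B reactivation is understated.** That needs a case coded to another term. Protocol 2.3 excludes carriers and patients with a history of hepatitis B, exclusion criterion 8 excludes positive serology, and an event coded to the infections class would still appear in the tables of SAP 16.1.7.2. Against this, the only scheduled hepatitis B test is the screening surface antigen, and a case the search does not retrieve would be absent from the reactivation table itself.

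**Conclusion.** The point holds for two categories. As written, SAP 16.1.10.8 and 16.1.10.10 can place events that are not autoimmune hepatitis or not chronic heart failure under those titles, in the count, the percentage and the patient-year rate. Overstatement is possible but not demonstrated, because the documents list neither the SMQ terms nor any expected cases.

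The figures in the working are simply one event divided by the exposure. They show that, for events this rare, one case can make up the whole category rate. They say nothing about how probable that case is.

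No primary or secondary endpoint changes. The hepatitis B search is a secondary point about sensitivity, and the documents do not allow it to be sized.

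**What to change.** - **16.1.10.8:** tabulate the preferred term *Autoimmune hepatitis* under that title, after checking it against the MedDRA version in use. Keep the existing SMQ output, retitled *Hepatitis, noninfectious (narrow SMQ)*.
- **16.1.10.10:** retitle the output *Cardiac failure (narrow SMQ)*. The search need not change.
- **16.1.10.1:** have the medical advisor also review any other hepatitis B-coded events for reactivation, or state why the single lowest-level term is sufficient.
- Keep the titles and searches aligned with the project-level integrated summary, so that the same event carries the same label in both.

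The cost is SAP wording, one additional small table, revised output titles, and medical review of a few hits, if there are any. It is best done before database lock.
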